## 6 SCHEDULE OF EVENTS

Study procedures are same for subjects enrolled in Phase 1 and Phase 2 (Table 4).

### 6.1. Screening Period (Post-transplant Day15 to Day100)

Subjects will be screened post autologous transplant after engraftment and up to day 100 of transplant which will qualify patients for study. Patients without adequate platelet count and/or WBC (see inclusion/exclusion criteria Sections 3.1 and 3.2) by day 100 will not be eligible for study.

A post-transplant bone marrow aspirate and biopsy will be required to document remission (defined here as <5% myeloblasts and CBC parameters as per Sections 3.1 and 3.2) before registration. Study procedures and information regarding the nature of the study will be reviewed with potential subjects and written informed consent will be obtained prior to any study related procedures. If deemed eligible, the following data will be obtained:

- Informed consent.

- Demographic information.
- Medical history, including previous treatment history (disease characteristics).
- A physical examination, including weight and height.
- Vital signs (blood pressure, heart rate and temperature) will be assessed after the subject has been supine for at least 3 minutes.
- Complete Blood counts with differential and serum chemistries (see Appendix D for details).
- Karnofsky performance status will be assessed. Data from Karnofsky status at initial diagnosis will also be obtained if available.
- Concomitant medications within four weeks prior to registration will be recorded.
- Adverse events will be assessed.
- Subjects will be instructed to avoid any restricted medications.
- 10ml of Bone marrow Aspirate will be sent to [name]'s laboratory (for shipping and handling instruction see Appendix C).
- Buccal Swab.
- Serum  $\beta$ -hCG for all female subjects. Serum  $\beta$ -hCG must be performed within 24 hours prior to prescribing lenalidomide. Subjects may not receive lenalidomide until the Investigator has verified that the results of these pregnancy tests are negative.

## 6.2. Treatment Period

### Cycle 1 - Day 1 (Week 1) visit:

All assessments must be completed prior to dosing with Lenalidomide. If Cycle 1 Day 1 date is no more than three days from screening laboratory assessments, then labs performed during screening may be used.

Assessments required for Cycle 1 Day 1:

- Physical Examination
- Karnofsky performance status
- Vital signs (blood pressure, heart rate and temperature)
- Complete Blood counts with differential and serum chemistries (see Appendix D for details).
- Concomitant medications assessment
- Adverse events assessment
- Start of Lenalidomide treatment

### Cycle 1 - Week 2 & Week 3 visits:

All assessments must be completed on planned day of the week ( $\pm 1$  day). Assessments required for Cycle 1 - Weeks 2 and 3:

- Physical Examination
- Karnofsky performance status
- Vital signs (blood pressure, heart rate and temperature)
- Complete Blood counts with differential and serum chemistries (see Appendix D for details).
- Concomitant medications assessment
- Adverse events assessment
- Lenalidomide treatment
- Review of Pill diary

**Cycle 1 – Week 4 visit:**

- Physical Examination
- Karnofsky performance status
- Vital signs (blood pressure, heart rate and temperature)
- Complete Blood counts with differential and serum chemistries (see Appendix D for details).
- Concomitant medications assessment
- Adverse events assessment
- Review of Pill diary

**Cycle 2 - Week 1 Visit:**

All assessments must be completed on planned day of the week ( $\pm 1$  day). Assessments required for Cycle 2 - Weeks 1 visit:

- Physical Examination
- Karnofsky performance status
- Vital signs (blood pressure, heart rate and temperature)
- Complete Blood counts with differential and serum chemistries (see Appendix D for details).
- Concomitant medications assessment
- Adverse events assessment
- Lenalidomide treatment
- Review of pill diary

**Cycle 2 - Week 3 Visit:**

All assessments must be completed on planned day of the week ( $\pm 1$  day). Assessments required for Cycle 2 - Weeks 3 visit:

- Physical Examination
- Karnofsky performance status
- Vital signs (blood pressure, heart rate and temperature)
- Complete Blood counts with differential and serum chemistries (see Appendix D for details).
- Concomitant medications assessment
- Adverse events assessment
- Lenalidomide treatment
- Review of pill diary

### **Cycle 3 and onward - Week 1 Visits:**

Beginning with cycle 3, study visits will be performed once every cycle, during the first week. Subjects will continue study treatment with Lenalidomide on *three-weeks-on, one-week-off* schedule. All assessments must be completed on planned day of the week ( $\pm 2$  days). Assessments required for Cycle 3 - Weeks 1 visit:

- Physical Examination
- Karnofsky performance status
- Vital signs (blood pressure, heart rate and temperature)
- Complete Blood counts with differential and serum chemistries (see Appendix D for details).
- Concomitant medications assessment
- Adverse events assessment
- Lenalidomide treatment
- Review of pill diary

### **Bone marrow biopsies**

Bone Marrow biopsy should be performed prior to or during Cycle 4 Week 1 visit, and should be repeated every four cycles during the first year, and every 6-8 cycles thereafter at the discretion of investigator, until disease progression.

### **6.3 End of Study Visit:**

An End of study visit should be performed within two weeks after last dose or subject's removal decision. Criteria for removal from the study are outlined on Section 5.4.

- Physical Examination
- Karnofsky performance status

- Vital signs (blood pressure, heart rate and temperature)
- Complete Blood counts with differential and serum chemistries (see Appendix D for details).
- Concomitant medications assessment
- Adverse events assessment
- Serum  $\beta$ -hCG for all female subjects.

#### **6.4 Follow-up period**

##### **Follow-up Visits:**

Any adverse event that occurred during the study treatment should be monitored by follow-up visits until it resolves to grade 1 or less, or until a new therapy is started. In case of an unresolved adverse event, a first follow-up visit must be scheduled no later than 30 days after end of study visit. Depending on the nature of the adverse events, follow-up visits should be scheduled regularly per investigator's discretion. If a subject is taken off the study before disease progression, bone marrow aspiration biopsies should be performed as described in Appendix C. Assessments required but not limited, during follow-up visits are;

- Physical Examination
- Karnofsky performance status
- Vital signs (blood pressure, heart rate and temperature)
- Complete Blood counts with differential and serum chemistries (see Appendix D for details).
- Concomitant medications assessment
- Adverse events assessment

##### **Phone follow-ups:**

After follow-up visits, subjects should be contacted to gather survival data every six months. Secondary malignancy information should also be obtained during phone follow-ups. Any secondary malignancy should be recorded and reported to coordinating center.

**Table 4:** Study Calendar

	Screening	Cycle 1 (Weeks)				Cycle 2 (Weeks)			Cycle 3	Cycle 4 & onward	End of Study 	Follow up Visits 	Phone Follow-up 
		W1	W2	W3	W4	W1	W2	W3					
Informed Consent	X												
Demographic Information	X												
Medical History	X												
Physical Examination	X	X	X	X	X	X		X	X	X	X	X	
Performance Status (KPS)	X	X	X	X	X	X		X	X	X	X	X	
Vital Signs	X	X	X	X	X	X		X	X	X	X	X	
CBC with differential 	X	X 	X	X	X	X		X	X	X	X	X	
Serum chemistry 	X	X 	X	X	X	X		X	X	X	X	X	
Concomitant Medications 	X	←----->											
Adverse Event Assessment 	X	←----->											
Buccal Swab	X												
Bone Marrow Aspiration Biopsy 	X									X 			
Lenalidomide Treatment		X	X	X		X	X	X	X	X			
Review of pill diary			X	X	X	X		X	X	X	X		
Urine $\beta$ -hCG 	X										X		
Instructions for restricted drugs 	X	←----->											
Secondary malignancy reporting												X	X
Survival Information												X	X

See next page for footnotes.

**Footnotes:**

1. Lab requirements are outlined in Appendix D.
2. Continuous collection of data during the study.
3. Must be performed at baseline, prior to or during Cycle 4 Week 1 visit, and be repeated every four cycles during the first year, and every 6-8 cycles thereafter in the discretion of investigator until disease progression.
4. If Cycle 1 Day 1 date is no more than three days from screening laboratory assessments, then labs performed during screening may be used.
5. Must be performed within two weeks after last dose or subject's removal decision.
6. Required for all female subjects. Must be performed within 24 hours prior to prescribing lenalidomide.
7. Any adverse event occurred during the study treatment should be monitored by follow-up visits until resolves to grade 1 or less, or until a new therapy is started. In case of an unresolved adverse event, first follow-up visit must be scheduled no later than 30 days after end of study visit. Depending on the nature of the adverse events, follow-up visits should be scheduled regularly per investigator's discretion. . If a subject is taken off the study before disease progression, bone marrow aspiration biopsies should be performed as described in Appendix C of protocol.
8. Subject must be contacted every six months.

## 7 CORRELATIVE/SPECIAL STUDIES

Correlative studies will be performed on all subjects. Specifically, our aims will include:

**Aim 1: To determine role of residual AML stem cells on efficacy of Lenalidomide maintenance after autotransplant.**

**Aim 2: To determine molecular markers of clinical response after Lenalidomide maintenance in AML**

Myeloid malignancies can arise from a small population of quiescent cancer-initiating cells that are not eliminated by conventional cytotoxic therapies. Eliminating leukemia stem cells can reduce the rates of relapse and increase leukemia free survival. Thus it is important to evaluate the role of persistent leukemia stem cells in the efficacy of Lenalidomide maintenance regimens.

**Aim 1: Analysis of AML stem cells pre and post treatment with lenalidomide and their correlation with response** (Study co-investigator [name] is an expert in flow sorting of leukemia stem cells and their functional characterization, both in vitro and in vivo). Using high-speed multi-parameter fluorescence-activated cell sorting we will separate bone marrow progenitors into long-term and short-term hematopoietic stem cells as well as more committed myeloid, erythroid and megakaryocytic progenitors, as performed previously. Sorted cells will have FISH studies done on them to estimate the number of stem cells with clonal cytogenetic alterations (Leukemic stem cells). Functional assays will also be done on these sorted cells to demonstrate clonogenic potential in vitro. A recently discovered marker of AML stem cells and putative predictor of overall survival, IL1RAP, will also be evaluated on AML stem cells and correlated with clinical response.

Our preliminary studies indicate that primitive stem cells (LT-HSCs and ST-HSCs) and certain progenitors (GMP) are expanded in AML and harbor initiating karyotypic abnormalities and striking alterations in DNA methylation with an accumulation of aberrantly hypermethylated loci.  Furthermore, we and others observe that karyotypically abnormal stem cells persist in the bone marrow even after morphological complete remission and thus may potentially lead to relapse of AML. These preliminary data lead us to hypothesize that a pool of disease-initiating stem or early progenitor cells exists in AML that contains and progressively acquires genetic and epigenetic alterations and may persist after conventional treatments. The study of these AML cells-of-origin and disease-initiating cell populations will reveal fundamentally new information about the persistence and elimination with lenalidomide maintenance treatment, Quantitative and cytogenetic assessment of AML stem and progenitor cells from marrow samples at the pretreatment and relapse stages will be performed. Karyotypic, transcriptomal, as well as methylomic analysis of these cells will be conducted to assess clonality and epigenetic profile . **Comparison of pretreatment and post treatment samples will demonstrate whether a decrease in clonal AML stem cells correlates with clinical response.** We will also determine whether persistence of clonal stem cells in responders correlates with a risk of future relapse.

Also, a recently discovered marker of AML stem cells, IL1RAP, will be evaluated on bone marrow aspirate cells, in combination with other known stem cell markers. IL1RAP expression on phenotypic stem cells and the frequency/kinetics of such cells upon treatment will be correlated with clinical outcomes.

#### **Aim 2: Molecular markers of relapse and remission:**

- a. Whole transcriptome and exome sequencing** of AML bone marrow stem and progenitors and correlation with response. Bone marrow aspirates will be used for these studies. Bone marrow stem cells will be sorted and RNA and DNA will be isolated. Sequencing libraries will be generated and subjected to massive parallel sequencing using an Illumina HiSeq2000 instrument. The transcriptome patterns will be correlated with response. In addition to gene expression patterns, this study will also correlate mutations and single nucleotide polymorphisms (from exome sequencing) with response to lenalidomide. Somatic mutations will be identified by comparison of marrow and germline (toenail clippings or cheek swabs) samples.
- b. Methylome profiling and clinical response:** DNA methylation has been shown to have clinical relevance and can be used to define AML patients into prognostic subgroups. DNA isolated from AML stem and progenitor cells will be used for global methylome analysis as done previously. Methylation patterns will be correlated with response and overall survival.

A bone marrow (BM) aspirate will be performed within the framework of the routine staging as outlined in Section 6.2. An extra tube of 10cc will be sent within 24 hours to the Albert-Einstein College of Medicine Department of Molecular Biology Laboratory where they will be processed and centrally analyzed. A detailed description of specimen collection, handling and shipping can be found in **Appendix C**.

In addition to bone marrow aspiration buccal swabs with brushes will be done at baseline and stored in RNA later solution. RNA/DNA will be isolated from these samples and compared to bone marrow samples to determine somatic mutations in AML stem cells.

## **8 MEASUREMENT OF EFFECT**

### **8.1 Response Assessment**

For the purposes of this study, subjects' bone marrow aspirate and biopsies will be used at regular intervals to assess progression. Please see Section 6.2 for the schedule.

### **8.2 Survival End Points**

#### **Progression-Free Survival**

Progression free survival (PFS) is defined as the duration of time from starting lenalidomide to time of progression.

**Progressive diseasea** is defined by the following:

- 5% myeloblasts on bone marrow aspirate and biopsy.

**Abbreviations:** CR, complete response; DFS, disease-free survival.

aAll relapse categories require two consecutive assessments made at anytime before classification as relapse or disease progression and/or the institution of any new therapy.

**Event-free survival (EFS):** The definition of an event is 1) disease progression or 2) death from any cause. EFS is the time from stem cell transplant until an event as defined above has occurred.

**TTP (Time to Progression):** This is the time from start of treatment to disease progression with deaths owing to causes other than progression not counted, but censored. This is a helpful method to assess the durability of treatment benefit.

**Overall survival (OS)** is defined as the time from transplant until death of any cause.

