**Statistical Considerations:**The aim of this proposal is to provide an accurate estimate of the two-year relapse free survival rate for elderly AML patients treated with lenalidomide maintenance after autologous stem cell transplantation. With approximately 30 patients, the study will be able to estimate the two year relapse free survival rate with not more than 9% standard error(i.e., if the observed rate is 40%, the 95% CI will be (23%, 56%). In addition, our study will have over 80% power to conclude that the two year relapse rate is significantly reduced when patients are treated with lenalidomide, assuming 60% and 90% patients will relapse with and without lenalidomide, respectively. The observed relapse free survival rate will be calculated along with its 95% CI. A one sample test on proportion will be used to detect if the relapse free survival rate with lenalidomide is significantly higher than that without the treatment (relapse rate is expected to be >95%).Secondary analysis including Kaplan-Meier analysis on overall survival.

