## **2.2 Autologous Stem Cell Transplantation as Consolidation Therapy for AML**

The antileukemic efficacy of autologous stem cell transplantation for AML has been well established for some time. Zittoun and colleagues randomized 623 AML patients in first remission to either further chemotherapy, allogeneic stem cell transplant or autologous stem cell transplant. Disease free survival at four years was 55% for allogeneic transplantation, 48% for autologous transplantation and 30% for intensive chemotherapy. The difference between autologous transplantation and chemotherapy was statistically significant. More recently, Vellenga and colleagues randomized over 500 patients with AML in first CR to either further intensive chemotherapy or autologous peripheral blood stem cell transplant. The transplant group showed a markedly reduced relapse rate (58% vs. 70%, P=.02) and better relapse free survival at 5 years (38% vs 29%, P=.065) Overall survival was similar because of more opportunities for salvage with second-line chemotherapy and stem cell transplantation in patients relapsing on the chemotherapy arm.

Autologous stem cell transplantation has also been studied in the elderly patient with AML. Lashkari and colleagues studied 27 patients aged 60-71 years with newly diagnosed AML in first CR. They underwent high dose chemoradiotherapy followed by

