## **10. STATISTICAL CONSIDERATIONS**

### **10.1 Study Design/Endpoints**

The aim of this proposal is to provide an accurate estimate of the two-year relapse free survival rate for elderly AML patients treated with lenalidomide maintenance after autologous stem cell transplantation. With about 30 patients, the study will be able to estimate the two year relapse free survival rate with not more than 9% standard error (i.e., if the observed rate is 40%, the 95% CI will be (23%, 56%). In addition, our study will have over 80% power to conclude that the two year relapse rate is significantly reduced when patients are treated with lenalidomide, assuming 60% and 90% patients will relapse with and without lenalidomide, respectively. The observed relapse free survival rate will be calculated along with its 95% CI. A one sample test on proportion will be used to detect if the relapse free survival rate with lenalidomide is significantly higher than that without the treatment (relapse rate is expected to be >95%). Secondary analysis including Kaplan-Meier analysis on overall survival.

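### Two-year relapse-free survival carries the aim, precision and only test but is never defined, and the raw proportion has no rule for patients followed for less than two years

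*Combined protocol and SAP*

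**What the plan says.** Section 10.1 opens with "The aim of this proposal is to provide an accurate estimate of the two-year relapse free survival rate for elderly AML patients", and the Synopsis repeats the text ("With approximately 30 patients, the study will be able to estimate the two year relapse free survival rate"). Precision is a standard error of at most 9% with about 30 patients. Power of over 80% is claimed for a different quantity: "the two year relapse rate is significantly reduced when patients are treated with lenalidomide, assuming 60% and 90% patients will relapse". The 60% applies to patients on the drug and the 90% to untreated patients. The test returns to RFS: "A one sample test on proportion will be used to detect if the relapse free survival rate with lenalidomide is significantly higher". The estimate is the observed rate with a 95% CI. Alpha and sidedness are not given. The only time-to-event method named is for another endpoint: "Secondary analysis including Kaplan-Meier analysis on overall survival".

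Section 8.2 defines four endpoints, and RFS is not among them:

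- **PFS:** "Progression free survival (PFS) is defined as the duration of time from starting lenalidomide to time of progression".
- **TTP:** from start of treatment to progression, with other deaths censored.
- **EFS:** progression or death from any cause, from transplant.
- **OS:** from transplant to death.

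On relapse ascertainment, Section 6.2 and Table 4 footnote 3 schedule marrows by treatment cycle until progression, and Section 8.1 refers back to that schedule. For patients who leave the study before progression, Section 6.4 and Table 4 footnote 7 call for marrows as set out in Appendix C. Appendix C covers specimen handling and shipping and gives no timing. Table 4 shows no marrow in the follow-up columns. The six-monthly calls collect survival and second malignancies.

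Section 10.2 projects 8 patients a year and completion in 45 months. Section 11.1 mentions a follow-up phase without giving its length.

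**The concern.** This is a single-arm trial with one test against a fixed benchmark, so the result depends on what counts as failure and when each patient is classified. Three things are left open.

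1. **The event.** It is not stated whether death in remission is a failure. PFS as written says no and so duplicates TTP. EFS says yes but starts at transplant and is not linked to RFS. Relapse rate and RFS are complements only if nobody dies in remission, yet power is stated on one and the test on the other.
2. **Incomplete follow-up.** An observed proportion needs a known two-year status for every patient. No rule covers those with less.
3. **Relapse after stopping drug.** The interval for looking is unclear, so late relapses can be missed or misdated.

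If these are settled after the data are seen, the same 30 patients could pass or fail.

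**Working it through.** **Inputs.** From Section 10.1: n=30; relapse 60% v 90%, that is relapse-free 40% v 10%; SE at most 9%. From Section 10.2: 8 patients a year, 45 months. Assumed, because the plan is silent: exact binomial test, one-sided 5%.

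**The plan's own figures.** SE at 40% = √(0.40×0.60/30) = 8.9%, as stated. Against 10%, P(X≥7)=0.0258, so the test rejects at 7 or more of 30. Power at 40% is 98.3%. Over 80% is correct as a lower bound.

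**Effect of the death rule on one data set.** Take 5 patients alive and relapse-free and 2 dead in remission at two years.
- Deaths counted as no relapse: 7/30 v 10%, p=0.026.
- Deaths counted as failures: 5/30 v 10%, p=0.18.

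The example sits on the cut-off, so it shows that a flip is possible, not that it is common.

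**Effect on power.** Hold relapse at 60% and add deaths in remission:

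| Die in remission | RFS | Power (≥7 of 30) |
|---|---|---|
| 0% | 40% | 98% |
| 4% | 36% | 95% |
| 5% | 35% | 94% |
| 10% | 30% | 84% |
| 15% | 25% | 65% |

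Power reaches 80% at RFS 28.7%, that is 40 − 28.7 = 11.3% dying in remission.

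**What the documents say about that rate.** Section 2.2 reports relapse and RFS as separate outcomes in a randomised comparison of transplant and chemotherapy: "markedly reduced relapse rate (58% vs. 70%, P=.02) and better relapse free survival at 5 years (38% vs 29%, P=.065". If both are five-year figures, the remainder is 100−58−38 = 4% in the transplant arm and 100−70−29 = 1% in the chemotherapy arm. This was not an elderly-only population.

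**Follow-up.** 30/8×12 = 45 months, so the projected duration equals accrual alone. If the analysis were at month 45 with even accrual, 30×(45−24)/45 = 14 patients would have 24 months. A proportion in those 14 has SE √(0.24/14) = 13.1%.

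Next, simulate all 30 at that cut with exponential event times (100,000 repeats, reject at 7 or more, evenly spaced or random uniform entry):

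| Event-free with under 24 months | Rejects at true RFS 10% | Rejects at true RFS 40% |
|---|---|---|
| Counted as successes | 68–71% | about 100% |
| Counted as failures | 0.02–0.04% | 31–32% |

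**Cost of the remedies.** Kaplan-Meier at month 45 (Greenwood, uniform accrual, 40% at 24 months) has SE 11.0%, against 8.9% with complete follow-up. Complete follow-up is reached at 45+24 = month 69 for 30 patients. Section 5 puts 30 in Phase 2 and 6 to 18 in Phase 1. If these are additional, accrual of 36 to 48 takes 54 to 72 months, and complete follow-up comes at months 78 to 96.

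**The case against.** **The power claim survives.** A reader might infer that over 80% power is wrong. It is not on the documents' own figures: the remainders in Section 2.2 are about 4% and 1%. The two elderly transplant series cited there report one transplant-related death in 27 patients and none, and patients enter this trial after transplant, in remission, with life expectancy above 12 months. Nothing points to 11%. This stands.

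**RFS has a customary meaning.** Section 2.2 uses it apart from relapse, which suggests that death counts. That makes one reading more likely, but Section 8.2 does not adopt it and supplies neither event nor time origin.

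**A third result from the same data is tempting.** 5/30 rejects against a 5% benchmark (p=0.016), and Section 10.1 also says "relapse rate is expected to be >95" per cent. That comes from the separate conflict between the 90% and >95% benchmarks. Against 5% both counts reject (7/30, p=0.0006), so the death rule changes nothing there.

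**Month 45 is not stated to be the analysis date.** Correct. The 14 of 30 and the error rates are conditional on it. What stands is that no date and no rule rule it out.

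**Marrows are scheduled until progression, not until drug stops.** This also stands in part: it would be too strong to say that off-drug relapse is not assessed. But the interval is counted in treatment cycles, and the off-study cross-reference leads to no schedule.

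**Section 5.4 and Section 8.2 serve different purposes.** The single-biopsy rule is a removal criterion; the two-assessment footnote classifies the endpoint. They are not a flat contradiction, so this is secondary.

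**Conclusion.** The point holds. The trial's main quantity has no event list, time origin or censoring rule, and PFS as written is not a survival endpoint because death in remission is not an event.

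The two consequences differ in size. The death rule matters for borderline results and costs little power if remission deaths are as rare as the background suggests. The missing follow-up rule matters more: under a month-45 analysis, the unstated choice moves type I error between about 0.04% or less and about 70%, and power at a true RFS of 40% between about 32% and 100%. False positives can therefore come from short follow-up and from missed off-drug relapses, as well as from a benchmark that counts deaths when the data do not.

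These figures assume n=30, an exact one-sided 5% test, a 10% null, even or uniform accrual and exponential event times. The documents do not support saying that the stated power is false, that off-drug relapse goes wholly unassessed, or that the analysis will be at month 45.

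**What to change.** 1. In Section 8.2, define RFS and PFS as time from first lenalidomide dose to relapse or progression, or death from any cause.
2. In Section 10.1 and the Synopsis, restate benchmark and power on that event and that time origin. Screening runs to day 100 after transplant, so a benchmark timed from transplant is not interchangeable.
3. Add relapse status and date to the six-monthly contact and Table 4 to at least 24 months, on or off drug. Correct the Appendix C cross-reference so that it leads to a stated schedule.
4. Estimate and test two-year RFS from the Kaplan-Meier curve with a log-log CI. Alternatively, state that the proportion is computed only once all analysed patients have 24 months of follow-up. Say whether Phase 1 patients are included.
5. Secondary: reconcile the removal criterion in Section 5.4, the footnote in Section 8.2 and the treatment-failure wording in Section 5.2, so that one stated rule dates the endpoint event.

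**Cost.** Mostly wording, one data field and no extra patients. The reported figures become slightly less favourable. Kaplan-Meier at month 45 has SE about 11%; keeping 9% means waiting to about month 69, or months 78 to 96 if Phase 1 patients are additional and included. A phone field captures only relapses diagnosed in routine care, and spelling out an off-drug marrow schedule may add procedures.

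### Overall survival is timed from transplant, but patients enter only after engraftment and documented remission, so the planned curve contains roughly 0.5 to 3.4 months per patient in which no death can be counted

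*Combined protocol and SAP*

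**What the plan says.** Section 8.2 uses two time origins.

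- **From transplant.** OS "is defined as the time from transplant until death of any cause". For EFS, "EFS is the time from stem cell transplant until an event as defined above has occurred".
- **From treatment.** "Progression free survival (PFS) is defined as the duration of time from starting lenalidomide to time of progression". For TTP, "This is the time from start of treatment to disease progression".

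Entry comes after transplant. Section 6.1 states: "Subjects will be screened post autologous transplant after engraftment and up to day 100 of transplant which will qualify patients for study". Its heading puts screening at day 15 to day 100. It also states: "A post-transplant bone marrow aspirate and biopsy will be required to document remission". Patients whose counts have not recovered by day 100 are not eligible. Section 3.1 repeats the remission and count requirements. Section 4.1 asks that treatment begin within 96 hours of registration.

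OS is secondary objective 1.2.3. Section 10.1 gives its analysis in one line: "Secondary analysis including Kaplan-Meier analysis on overall survival". No section mentions delayed entry, left truncation or a landmark.

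**The concern.** A patient who dies between transplant and registration cannot be in the data set. For every patient who is in it, that interval still counts as survival time. The OS curve therefore cannot fall during the interval, whatever lenalidomide does, and patients who enter later bring more of this time.

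Objective 1.2.3 can be read in two ways, and the curve fits neither. If it means survival on maintenance, the clock starts too early. If it means survival after transplant plus maintenance, the clock is arguable, but the early deaths are missing and the plan does not describe the curve as conditional on reaching registration in remission.

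The trial has one arm, so its OS curve can be read only against outside figures such as those in Section 2.2. An upward shift that would appear with an inactive drug could then be taken for benefit. PFS and OS would also be reported from different starting points, so their medians could not be set side by side.

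**Working it through.** **The plan's own figures.** The plan gives no expected OS. Its precision figure is for two-year relapse-free survival: at 40% with 30 patients, SE = sqrt(0.40 × 0.60 / 30) = 8.9%, which agrees with the stated limit of 9%. It serves below as a yardstick.

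**Guaranteed time (L).** The earliest screening day is 15, and 15 / 30.44 = 0.5 months. The latest first dose is taken as day 100 plus 96 hours, which is day 104, and 104 / 30.44 = 3.4 months. Day 104 is inferred from Sections 6.1 and 4.1 and is not a stated limit.

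**Comparison A: survival from first dose.** If S(t) is survival from first dose and a patient starts at L after transplant, the curve timed from transplant is S(t − L). The median moves up by the whole of L. Assume S(24 months) = 40% and a constant hazard:

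- hazard = −ln(0.40) / 24 = 0.0382 per month
- reported two-year rate = exp(−0.0382 × (24 − L))

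| First dose, day after transplant | L (months) | Reported rate | Excess (points) |
|---|---|---|---|
| 15 | 0.49 | 40.8% | 0.8 |
| 60 | 1.97 | 43.1% | 3.1 |
| 100 | 3.29 | 45.4% | 5.4 |
| 104 | 3.42 | 45.6% | 5.6 |

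Each row supposes that all patients start on that day. A true 28% would be reported as 28.7% to 33.6%, and a true 10% as 10.5% to 13.9%, over days 15 to 104. This shift does not depend on how many patients die early.

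**Comparison B: survival from transplant in all transplanted patients.** Enrolled patients are conditioned on being alive at L, so the reported rate is S(24) / S(L). Section 2.2 cites 28% three-year OS in 27 autografted patients aged 60 to 71. Assume that figure runs from transplant, with a constant hazard:

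- hazard = −ln(0.28) / 36 = 0.0354 per month
- S(24) = exp(−0.0354 × 24) = 42.8%
- entry at day 57 (about mid-window): exp(−0.0354 × 22.13) = 45.7%, a gain of 2.9 points
- entry at day 100: exp(−0.0354 × 20.71) = 48.1%, a gain of 5.3 points

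This hazard implies 1 − exp(−0.0354 × 3.29) = 11% dead by day 100. The same cohort had one transplant-related death in 27 (3.7%). If early deaths were that few, the reported rate would be 42.8% / (26/27) = 44.4%, a gain of 1.6 points.

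**The case against.** The strongest reply is that nothing in the trial turns on this. OS is a secondary endpoint with no hypothesis, threshold or power statement. The planned test concerns two-year relapse-free survival, and PFS and TTP start with treatment. The origin is stated openly, so a reader can see what is measured. With 30 patients the SE at 43% is sqrt(0.43 × 0.57 / 30) = 9.0 points, so a gain of 3 to 5 points is only about 0.3 to 0.6 SE. All of this stands, and it limits the weight of the point. It does not remove the bias, which always runs upward and does not shrink with more patients.

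The size is also open to challenge, and the challenge succeeds in part. The constant hazard behind the 3 to 5 points implies more early deaths than the transplant-related mortality cited in Section 2.2. Transplant-related deaths are not all early deaths, so 1 in 27 is not a firm figure either. Section 2.2 does not say from when the 28% is timed, and the documents give no distribution of entry times. A reader might take 3 to 5 points as the established bias. The documents support only a range that depends on the assumptions.

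A reader might also infer that two planned curves, OS and EFS, are affected. EFS is defined in Section 8.2 but is not listed as an objective and does not appear in Section 10. For EFS this is a flawed definition, not a flawed planned analysis.

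Finally, delayed entry is not a clean remedy. It needs entry time to be unrelated to prognosis, which is doubtful if late entry reflects slow count recovery, and it does not remove the selection on remission. With about 30 patients, the early risk sets would also be small. This stands, and is why re-timing from first dose comes first.

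**Conclusion.** The point holds for OS. Timing from transplant while enrolling only survivors in remission builds in roughly 0.5 to 3.4 months per patient during which no death can be counted. The resulting curve overstates survival on maintenance, and it overstates survival after transplant in all transplanted patients.

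Against survival from first dose, the excess at two years is 0.8 to 5.6 points if the true rate is 40%, the hazard is constant and entry falls between day 15 and day 104. Against all transplanted patients, it is about 1.6 points with early deaths near 1 in 27, and 3 to 5 points under a constant hazard with entry at day 57 to 100. The 40%, the constant hazard, the entry days and the transplant origin of the cited 28% are assumptions.

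It is tempting to conclude that the primary test is biased too. The documents do not support that: Section 10.1 gives no time origin for two-year relapse-free survival. That omission needs its own answer, but it does not show that the transplant origin applies there.

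The change should be made because it costs almost nothing and the curve will be read against outside figures. It does not threaten the trial's main conclusion.

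**What to change.** In Section 8.2, define OS from the first dose of lenalidomide to death from any cause, the same origin as PFS and TTP. Do the same for EFS if it will be reported; otherwise state that it will not be analysed. Name the origin in the Kaplan-Meier sentence of Section 10.1.

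If survival from transplant is also shown, present it as supplementary and label it as conditional on reaching registration in remission. Delayed entry at the first-dose date may be used, with a stated caveat that entry time may be related to prognosis and that early risk sets will be small. Reporting the distribution of the transplant-to-dose interval would let readers judge the shift.

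The cost is wording in two sections. The transplant date is already needed for the current definitions and the screening window, and the first-dose date for PFS. No visit or treatment rule changes. The downside is that each patient's reported OS becomes shorter by the transplant-to-dose gap, about 0.5 to 3.4 months. A patient registered but never dosed would have no OS time, as is already so for PFS; Section 4.1 allows such registrations to be cancelled.
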